3.3 Study treatments and assessments

The maximum study duration from Screening period to end of the safety follow-up period is 20 weeks. The duration of treatment is 12 weeks.

EDP-305 will be supplied as 1 mg and 2.5 mg tablets for oral administration; doses administered will be 1 mg, 2.5 mg or placebo taken once daily (QD) for 12 weeks.

The subject will be instructed to take all study drug doses at home except when study drug will be administered in the clinic (i.e., at the Days 1 and 3, and Weeks 2, 4, 8 and 12 visits). The subject will be instructed to take the study drug approximately at the same time every day (i.e., orally in the morning after fasting overnight for a minimum of 8 hours). If a subject forgets to take their study drug at their scheduled time, the dose may be taken later that day following a minimum of 4 hours fast; however, no more than 1 dose should be taken on any calendar day and a minimum of 16 hours between doses should be maintained.

A detailed description of procedures and assessments to be conducted during this study is summarized in the Scheduled of Study Assessments in the table below.

Table 2: Schedule of Study Assessments

Study Event	Screening ¹	Study Assessments per Planned Study Day						EOS
Visit Day	D-28 to -1	D1 ²	D3	D14±2	D28±2	D56±2	D84±3 ³	D112±2
Treatment Week⁴				W2	W4	W8	W12/EOT ⁵	W16
ICF ⁶ ; Demography; Medical History	x							
Inclusion/Exclusion	x							
FSH ⁷ ; HIV, HCV, and HBV	x							
Pregnancy Test ⁸	x	x			x	x	x	x
Height, Weight and BMI ⁹	x	x					x	x
Physical Exam ¹⁰	x	x	x	x	x	x	x	x
Vital Signs ¹¹	x	x	x	x	x	x	x	x
Oral Temperature	x	x						x
ECG	x	x	x		x		x	
Waist to Hip Ratio		x					x	
Safety Lab. Tests ¹²	x	x	x	x	x	x	x	x
PT/PTT and INR	x							x
CV Markers ¹³		x		x	x	x	x	x
MRI-PDFF, MRE	x						x	
ELF Panel, PRO C3, Inflammatory Markers ^{14, 15}		x					x	
APRI, FIB-4, and NFS		x					x	
FGF-19, C4, BA, and ALT ¹⁶		x		x	x	x	x	
PK/PD sub study (PK, C4, FGF-19, BA, and ALT) ¹⁷		x		x	x	x	x	
Population PK samples ¹⁸		x		x	x	x	x	
CK-18 and GLP-1 ¹⁵		x		x	x	x	x	
Study Drug Dosing ¹⁹		Daily Dosing						
Drug Accountability			x	x	x	x	x	
AE/SAE & Con Meds	x	x	x	x	x	x	x	x
Exploratory research samples ¹⁵		x			x	x	x	

1. Screening assessments should be conducted within 28 days prior to the first dose of study drug (i.e., Study Days -28 to -1)

2. On Day 1, all samples are to be collected predose with the exception of post dose PK and PD samples

3. Subjects should discontinue drug on Day 84. Subjects who return for their EOT Visit after Day 84, should stop dosing on Day 84
4. For the treatment phase, indicates number of completed weeks of treatment
5. For the EOT visit for subjects who discontinue early, all procedures for the Week 12 visit will be conducted; however, an MRI /MRE will not be performed if the subject has discontinued study drug prior to Day 14 and only 1 PK sample will be obtained. Subjects who discontinue the study early should complete the EOT procedures as soon as possible and return 4 weeks later for the EOS visit. For subjects with persistent transaminase elevations and who discontinue study drug with evidence of liver injury, additional PK samples will be collected at each visit where safety labs are obtained
6. Informed consent must be obtained prior to conducting any study-specific procedures or assessments
7. For post-menopausal women only
8. Serum pregnancy test at Screening and Baseline, and urine pregnancy testing at Baseline and all other visits. If the urine pregnancy test is positive, a serum pregnancy test should be obtained as soon as possible to confirm.
9. Height to be assessed at Screening only
10. Full physical exam (PE) at screening and EOS Visit; subsequent PE should be targeted to review new signs and symptoms
11. Vital Signs include heart rate, respiratory rate, blood pressure, and will be measured once in the morning before the morning dose of study drug
12. Safety laboratory tests include chemistry (including liver function tests), hematology, and urinalysis and should be collected predose at all visits; See Table 2 for details. Creatinine clearance will be calculated based on serum creatinine value performed all visits. HbA1c will be obtained at Screening, Baseline, and Week 12 only
13. Lipids and CV risk markers to be collected are detailed in Table 2
14. Markers of inflammation include fibrinogen, CRP, IL6, IL1 β , TNF- α , TNF- β , alpha2 macroglobulin and haptoglobin (See Table 2)
15. Samples will be collected from all subjects predose Additional samples may be collected to further assess safety events
16. Samples should be collected after a minimum 8 hr fast and before the subject takes the daily dose of study drug. All samples collected Day 1, Weeks 2, 4, 8 and 12 at predose and two samples post dose; with the first sample collected 1 to 3 hours postdose and the second sample collected at least 1 hour later
17. Collect PK/PD samples after a minimum 8 hr fast and before the daily dose of study drug. PK/PD samples on Days 1 and 84 (Week 12) collected predose and 2, 6, and 8 hr post dose; Weeks 2, 4 and 8 at predose and two samples post dose with the first sample collected 1 to 3 hours postdose and the second sample collected at least 1 hr late
18. PK predose samples should be collected after a minimum 8 hour fast before the daily dose of study drug. PK samples collected Day 1, Weeks 2, 4, 8 and 12 at predose and two samples post dose; the first sample collected 1 to 3 hours postdose and the second sample at least 1 hour later. For subjects with persistent transaminase or ALP elevations and have evidence of liver injury and who remain on study drug, additional PK samples will be collected at each visit where safety labs are obtained.
19. Study drug given in the clinic on days where subject is seen in the clinic

4 STUDY ENDPOINTS

4.1 Primary efficacy endpoint(s)

The primary efficacy endpoint of the study is the change from Baseline in ALT levels at Week 12.

4.2 Secondary efficacy endpoint(s)

The secondary efficacy endpoints are as follows:

- Change from Baseline in percentage of fat in the liver as assessed by MRI-PDFF at Week 12
- Change from Baseline in liver stiffness as assessed by magnetic resonance elastography (MRE) at Week 12
- Change from Baseline of noninvasive liver fibrosis markers (ELF panel) and PRO C3 at Week 12
- Change from Baseline in NFS, APRI, and FIB-4 at Week 12
- Change from Baseline in TG, TC, HDL-C, LDL-C, adiponectin, and ApoA1, B, C3 at Week 12
- Change from Baseline in fasting glucose and insulin, HOMA index (in nondiabetic subjects) and HbA1c in subjects with T2DM at Week 12
- Change from Baseline in fibrinogen, CRP, IL6, IL1 β , TNF- α , TNF- β , alpha2 macroglobulin and haptoglobin levels at Week 12
- Pharmacokinetic parameters of EDP-305 (and metabolites): C_{max} , T_{max} , and AUC_{last}
- Change from Baseline in body weight at Week 12
- Change in waist to hip WTH ratio at Week 12
- Pharmacodynamic parameters of EDP-305: FGF19, C4, and bile acid (BA) at Week 12

In addition, the percentage change from Baseline in the primary endpoint and all secondary endpoints will be summarized (as applicable).

4.3 Safety endpoint(s)

The primary safety endpoint of the study is the frequency of Adverse Events (AEs), Serious Adverse Events (SAEs), and AEs leading to discontinuation through Week 12

5 SAMPLE SIZE AND POWER

Group sample sizes of 44 (in each dose group) and 22 placebo subjects achieves 80.438% power to reject the null hypothesis of equal means when the population mean difference in ALT is $(-40.0) - (-10.0) = -30.0$ with a standard deviation for both groups of 40.0 and with a significance level (alpha) of 0.050 using a two-sided two-sample equal-variance t-test. To account for a 10% discontinuation rate, 15 additional subjects will be enrolled to attempt to have at least 110 subjects who complete treatment bringing the total number of subjects enrolled to 125.

6 ANALYSIS POPULATIONS

6.1 Safety population

All subjects who receive at least one dose of study drug. Subjects will be included in the treatment group that corresponds to the study drug received during the study.

6.2 Efficacy population

All subjects who receive at least one dose of study drug. Subjects will be included in the randomized treatment group.

Subjects will be included in the analysis according to the treatment to which they were randomized.

6.3 Per protocol population

All subjects in the efficacy population who enter the study without a protocol violation and did not have a major (key) protocol deviation as defined below will be included in the per protocol population. This population will be reviewed and finalized prior to locking the database and unblinding the study.

6.4 Pharmacokinetic population

All subjects receiving active study drug and having any measurable plasma concentration of study drug at any timepoint.

Subjects will be included in the analysis according to the study drug received during the study.

6.5 Protocol deviations and exclusion from Per protocol analysis aet

Protocol deviations will be identified following the [REDACTED], and after review and validation of the Enanta study team prior to locking the database and unblinding the treatment codes. If necessary, a meeting will be held to discuss and adjudicate any deviations that need classification (major vs. minor). Deviations will be identified using data listings provided by [REDACTED] and from the deviation log maintained by [REDACTED].

The listing of protocol deviations will be reviewed by Enanta team with focus from Biometrics/Medical in order to define the Per Protocol population. Subjects with a protocol violation or a major protocol deviation will be thus identified for exclusion from the per protocol population.

7 STATISTICAL CONSIDERATIONS AND ANALYSIS

7.1 Derived variables

The below table provides the list of derived variables for demographic and baseline characteristics, various duration derivations, drug compliance, baseline derivations and other important derivations applicable for this study.

Table 3.

Variables	Formula
Demographic and Baseline characteristics	
Age at informed consent (in years)	floor ((date of informed consent – date of birth + 1)/ 365.25)
Body mass index (BMI) (kg/m ²)	weight (kg) / [height (m)] ²
Derivation of Duration	
Study day at any visit	Date of interest – date of first dose of study drug. One day is added if this difference is ≥ 0
Extent of Exposure (Days)	Date of last randomized study drug intake – Date of first randomized study medication intake + 1
Extent of Exposure (Weeks)	Extent of exposure (days)/7
Drug Compliance	
Compliance	$100 \times [1 - (\text{Number of days of study drug interruption}) / (\text{Extent of exposure (days)})]$
Baseline Derivations	
Baseline (Average)	The average of the screening and the day 1 values.
Baseline (Last value pre-dose)	Last non-missing values collected prior to the first dose of study drug
Screening	The value obtained at screening.
Change from Baseline	Post Baseline value – Baseline
Percentage change from Baseline	$[(\text{Change from Baseline}) / \text{Baseline}] * 100$
Other Derivations	
Creatinine Clearance (Cockcroft-Gault)	$CL_{Cr} (\text{mL/min}) = \{((140 - \text{age [years]}) \times \text{weight}) / (72 \times S_{Cr})\} \times 0.85$ (if female). S_{Cr} = serum creatinine
AST to Platelet Ratio Index (APRI)	$APRI = ([\text{AST (IU/L)} / \text{AST ULN (IU/L)}] / [\text{Platelets}(10^9/\text{L})]) \times 100$

	ULN = upper limit of normal
Fibrosis-4 score (FIB-4)	$FIB-4 = [Age \text{ (years)} \times AST \text{ (IU/L)}] / [Platelets \text{ (} 10^9/L) \times (\sqrt{ALT \text{ (IU/L)}})]$
NAFLD fibrosis score (NFS)	$NFS = -1.675 + 0.037 \times Age \text{ (years)} + 0.094 \times BMI \text{ (kg/m}^2) + 1.13 \times IFG/Diabetes \text{ (yes = 1, no = 0)} + 0.99 \times AST/ALT \text{ ratio} - 0.013 \times Platelets \text{ (} 10^9/L) - 0.66 \times Albumin \text{ (g/dL)}$

7.2 Definition and use of visit windows in reporting lab, vital signs

Note that Day 1 in the table below is taken as the first day of dosing with study drug. It may not be the same as the first study date which is the randomization date. Also note that Day 0 does not exist, so Day -1 is the day before Day 1. Also, the relative days (rel_day) from Day 1 are defined as the visit date minus first dosing date plus one. For treatment-free follow-up period, the rel_days is computed from the date of last dose. Unless otherwise specified in specific analyses, the analysis visit windows will follow the rules in the following table.

Table 4.

Analysis Visit No.	Analysis Visit Label	Target Day	Visit Window
1	Screening	N/A	$-28 \leq rel_day \leq -1$
2	Baseline	1	Rel_day= 1*
3	Day 3	3	Rel_day= 3
4	Week 2	14	$4 < rel_day \leq 21$
5	Week 4	28	$22 \leq rel_day \leq 42$
6	Week 8	56	$43 \leq rel_day \leq 70$
7	Week 12	84	$71 \leq rel_day \leq \text{end of treatment} + 7$
8	Follow-up Week 4	21**	$\text{End of treatment} + 7 \leq rel_day < \text{end of study}$

* Baseline analysis visit window may be considered as $Rel_day \leq 1$ in some analyses (e.g., those involving change from Baseline). That is, in case that Day 1 observation is missing, the last non-missing observation before or on the first dosing date may be considered as

the Baseline. For Lab values, average of all values collected prior to the first dose of study drug will be considered Baseline.

** computed from the date of last dose.

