7.1.5. Safety Follow-up Period (End of Study Visit)

All subjects, including those who discontinue treatment early, should return to the clinic for the EOS visit 4 weeks after the last dose of study drug for follow-up safety assessments (Table 19). For subjects who complete the study, the EOS visit would be scheduled on Day 112.

Any subject with ongoing AEs/SAEs at the EOS visit should be followed until resolution of their AE/SAE or until the Investigator has determined that the event has stabilized as discussed in Section 9.3.

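### SAP Table 4 leaves an on-time completer's end-of-study visit outside the follow-up window and does not keep off-drug values out of the Week 2, 4 and 8 windows

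*SAP*

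**What the plan says.** SAP 7.2 sets the default analysis windows for laboratory and vital-sign data (Table 4).

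- **On-treatment clock:** "the relative days (rel_day) from Day 1 are defined as the visit date minus first dosing date plus one".
- **Follow-up clock:** "For treatment-free follow-up period, the rel_days is computed from the date of last dose". Whether one day is added here too is not stated.
- **Follow-up row:** "Follow-up Week 4" has target day 21, footnoted as counted from the last dose. It runs from end of treatment + 7, inclusive, to strictly before end of study. Table 4 does not define end of study.
- **On-treatment rows:** Day 3 is exactly Day 3. Week 2 is above Day 4 through Day 21, Week 4 is Days 22 to 42, and Week 8 is Days 43 to 70. Week 12 runs from Day 71 to end of treatment + 7, inclusive.
- **Day numbering:** SAP 7.2 says "Also note that Day 0 does not exist, so Day -1 is the day before Day 1". SAP Table 3 (7.1) has its own study-day rule: "One day is added if this difference is ≥ 0".

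Protocol 7.1.5 says that all subjects, early discontinuers included, "should return to the clinic for the EOS visit 4 weeks after the last dose of study drug". For completers that is Day 112, with ±2 days in the Schedule of Assessments. No other post-treatment visit is scheduled.

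**The concern.** The follow-up row exists to hold one visit, and as written it appears to miss it. Its target day does not match the timing of EOS, its upper bound is strict at the point where EOS falls, and the section uses two clocks without saying which governs the bounds.

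The on-treatment rows have a related weakness. Week 12 stops 7 days after treatment ends, but Weeks 2, 4 and 8 have no such limit. Nothing in Table 4 therefore stops a value taken four weeks off drug from being labelled as an on-treatment visit.

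At stake are the by-visit outputs for data collected at EOS: safety laboratory tests (ALT, AST, bilirubin, GGT and alkaline phosphatase among them), lipids and cardiovascular markers, weight and vital signs. SAP 8.6.2, 8.6.3.5, 8.6.3.8 and 8.6.4.1 plan least-squares means and p-values by visit for ALT, lipids, weight and the other liver tests. Follow-up summaries could be empty, and Week 4 or Week 8 estimates could mix on-drug and off-drug values.

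**Working it through.** **1. Target day.** EOS Day 112 − last dose Day 84 = 28. Table 4 gives 21 from the last dose, which does not reproduce. It would be right for a count starting at end of treatment + 7 (28 − 7 = 21), but the footnote does not say that.

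**2. Does a completer's on-time EOS enter the follow-up row?** Last dose is Day 84, EOS is Day 112, and end of study is taken as the subject's EOS visit.

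| Reading | Test | In the row? |
|---|---|---|
| Day and bounds from first dose | 91 ≤ 112 < 112 | No |
| Day and bounds from last dose | 7 ≤ 28 < 28 | No |
| Day from last dose, bounds from first dose | 91 ≤ 28 < 112 | No |

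If end of study means nominal Day 112 (first-dose clock), visits on Days 110 and 111 are in and Days 112 to 114 are out. EOS gets in only if the two bounds are put on different clocks (7 ≤ 28 < 112), or if end of study is some date after the visit. The SAP states neither.

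**3. Early discontinuers in the follow-up row.** With last dose on Day L, EOS is Day L + 28. On the first two readings the strict bound excludes EOS for every L. On the third the test is L + 7 ≤ 28 < L + 28, which admits EOS for L = 1 to 21.

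**4. Overlap.** Day 84 + 7 = 91 satisfies both the Week 12 upper bound and the follow-up lower bound.

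**5. Missing cap on Weeks 2, 4 and 8.** If EOS is placed on the first-dose clock:

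- L = 1 to 14 gives Days 29 to 42, which is Week 4.
- L = 15 to 42 gives Days 43 to 70, which is Week 8.
- L = 43 to 84 gives Days 71 to 112. Week 12 ends at L + 7, so EOS is in no window.

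With EOS 26 or 30 days after the last dose, the two cut-offs move by 2 days (16 and 44, or 12 and 40). If the early EOT visit is held on the last-dose day, it falls in an earlier window than EOS, so EOS is that subject's only record there.

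On the last-dose clock EOS is day 28 (29 if one day is added) for every subject. Week 8 is then impossible, but 28 lies within 22 to 42. It therefore fits Week 4 numerically, for completers too, unless follow-up records are confined to the follow-up row.

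**6. Gaps and Day 0.** Days 2 and 4 are in no window. For the day before dosing, the SAP 7.2 formula gives −1 + 1 = 0, which that section says does not exist; SAP Table 3 gives −1. A record labelled 0 also misses the Screening window (−28 to −1).

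**7. Numbers of subjects.** Total discontinuation is 20% in Protocol 11.2 (0.20 × 125 = 25) and 10% in SAP 5 (0.10 × 125 = 12.5). Only subjects stopping by Day 42 could put EOS in an on-treatment window under step 5, first-dose clock. The documents give no timing. If stopping were uniform over 84 days (an assumption), half would qualify: about 6 to 12 subjects over all arms.

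**The case against.** The strongest reply is that the intent is clear and other sections carry it.

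- SAP 8.7.3 places laboratory abnormalities more than 7 days after the last dose in treatment-free follow-up. SAP 8.7.1 uses the same 7-day boundary for AEs. Table 4 is a default that specific analyses may override. This stands: those tables are protected.
- A reader might infer that off-drug EOS values will enter Weeks 4 and 8. The documents do not support that as a certainty. The split needs the first-dose clock, and SAP 7.2 puts follow-up data on the last-dose clock. What stands is that the allocation is ambiguous and no cap guards against it.
- A reader might also infer that EOS is lost for everyone. On the mixed-clock reading, subjects stopping by Day 21 are admitted.
- The strict sign may be a typographical slip, and the source file is worth checking. With ≤, a completer's EOS passes on the first-dose clock (91 ≤ 112 ≤ 112). The target day, the overlap, the missing cap and the two clocks would still need correcting.
- Calling Day 0 an uncovered day goes too far. It arises only from a formula that conflicts with SAP Table 3, and the baseline footnote (relative day ≤ 1) recovers such values in some analyses.
- Days 2 and 4 are off-schedule, because the Day 3 visit has no tolerance, and SAP 8.1 sends unscheduled results to listings. That gap is minor.

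**Conclusion.** Table 4 needs correcting. An on-time completer's EOS does not enter the follow-up row whichever clock its two bounds share, given that end of study is the subject's EOS visit or nominal Day 112. The target day is 7 days short, Day EOT + 7 is in two rows, and Weeks 2, 4 and 8 lack the cap that Week 12 has.

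The reach is limited. Exposed are by-visit laboratory, lipid, weight and vital-sign summaries and the by-visit ANCOVAs on those data. Observed Week 12 ALT is not affected, because no EOS value at L + 28 can pass a limit of L + 7. ELF, PRO-C3, inflammatory markers, imaging, CK-18, GLP-1 and ECG are not scheduled at EOS.

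Two larger conclusions are not supported. Neither 25 of 125 subjects nor any other count can be given as the number affected, since the two documents disagree on the discontinuation rate and neither gives its timing. An unequal effect across arms is possible but not shown.

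**What to change.** Rewrite Table 4 as follows.

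- **Follow-up:** on the last-dose clock, more than 7 days after the last dose through the EOS visit inclusive, target day 28. State whether one day is added.
- **On-treatment windows:** cap each at last dose + 7 days, as Week 12 already is and in line with SAP 8.7.3. No EOS value at L + 28 can then enter one, and the Day EOT + 7 overlap disappears.
- **Gaps:** for example, Day 3 = Days 2 to 4 and Week 2 = Days 5 to 21.
- **Day numbering:** replace the SAP 7.2 formula with the SAP Table 3 rule, so that Day 0 cannot arise.

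The cost is SAP wording and programming. No data collection changes, and SAP 1 provides for an amended version before database lock.

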7.3 Handling of missing data and outliers

7.3.1 Missing data analysis methods

In general, missing data for the primary endpoint and secondary endpoint are not imputed, with the exception being a secondary analysis on the primary endpoint. The extent and pattern of missing data for primary endpoints will be summarized by treatment group. All missing Week 12 values for the primary efficacy endpoint will be estimated by multiple imputation (MI). The Markov Chain Monte Carlo (MCMC) method (*Dong et al, 2013*) will be used to impute the missing Week 12 values. The least squares mean and standard error for the change from Baseline in Week 12 analysis values will also be derived from an analysis using the MCMC method of MI.

Multiple Imputation Method

MI handles missing data in three steps:

Step 1: Imputation using MCMC Method

For MI analysis first uses MCMC method to impute the missing data through SAS Proc MI. The goal of the imputation step is to draw random samples of missing data based on information contained in the observed data. Since the parameter (θ) of the data is also unknown, the imputation step actually draws random samples of both missing data and θ based on the observed data.

The MCMC method draws samples in two steps. At step one (I-Step), given the current estimate of $\theta(t)$ at the t^{th} iteration, a random sample Y_{miss}^{t+1} is drawn from the conditional predictive distribution of $P(Y_{mis}|Y_{obs}, \theta^t)$. At step two (P-step), given Y_{miss}^{t+1} , a random sample of $\theta^{(t+1)}$ is drawn from the distribution of $P(\theta|Y_{obs}, Y_{mis}^{t+1})$. Starting with an initial value $\theta^{(0)}$ (usually an arbitrary guess), MCMC iterates between the I-step and the P-step, leading to a Markov Chain:

It can be shown that this Markov Chain converges in distribution to $P(\theta, Y_{mis}|Y_{obs})$. It follows that the sequence $\theta(1), \theta(2), \dots, \theta(t), \dots$ converges to $P(\theta|Y_{obs})$ and the sequence $Y_{mis}^1, Y_{mis}^2, \dots, Y_{mis}^t, \dots$ converges to $P(Y_{mis}|Y_{obs})$. Thus, after the Markov Chain converges,

m draws of Y_{mis} can form m imputations for the missing data. At the end of the first step in MI, missing data will be imputed m times to produce m sets of complete data.

Step 2: Statistical Analysis

The second step of MI analyzes the m sets of data separately using Proc Mixed to estimate the relevant standard errors and least square means. At the end of the second step, m sets of parameter estimates are obtained from separate analyses of m data sets.

Step 3: Combining Results

The third step of MI combines the m estimates into one using PROC MIANALYZE.

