11.5. Efficacy Endpoints

11.6. Primary Efficacy Endpoints

The primary efficacy endpoint of the study is the change from baseline in ALT at Week 12. All subjects in the efficacy population will be included. Comparisons of treatment arms will be performed using an analysis of covariance (ANCOVA) model with treatment and baseline values included in the model where appropriate. Multiple Imputation (MI) will be used to impute missing data. Details will be provided in the SAP.

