1 INTRODUCTION

The Statistical Analysis Plan (SAP) describes the statistical methods to be used during the reporting and analyses of data collected under Enanta Pharmaceuticals, Inc. Protocol EDP 305-101 entitled “*A Phase 2 Dose Ranging, Randomized, Double Blind, and Placebo-Controlled Study Evaluating the Safety, Tolerability, Pharmacokinetics and Efficacy of EDP-305 in Subjects with Non-Alcoholic Steatohepatitis (NASH)*”.

This SAP should be read in conjunction with the study protocol and case report form (CRF). This version of the plan has been developed using the protocol version 3.0 dated 21Feb2018 (Amendment 2.0) and CRF dated 2NOV2018. Any further changes to the protocol or CRF may necessitate updates to the SAP.

Changes following approval of this SAP will be tracked in the SAP Change Log and a final amended version will be issued for Sponsor approval prior to database lock, and subsequent unblinding of treatment codes, efficacy lab and imaging data for final study results delivery.

Any change to the data analysis methods described in the protocol will require an amendment only if it changes a principal feature of the protocol. Any other change to the data analysis methods described in the protocol, and the justification for making the change, will be described in the clinical study report. Additional exploratory analysis of the data may be conducted as deemed appropriate.

The preparation of this SAP has been based on International Conference on Harmonization (ICH) E9 guidelines. The table of contents and shells for the tables, figures and listings (TFLs) will be produced in a separate document. All data analyses and generation of TFLs will be performed using SAS 9.3® or higher.

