8.6.2 Analysis of primary efficacy endpoint(s)

The primary efficacy endpoint of the study is the change from Baseline in ALT at Week 12. All subjects in the efficacy population will be included, with a secondary analysis

performed on the per protocol population.

Baseline in ALT will be derived based on three different methods (see Table 3): Baseline (Average), Baseline (Last value pre-dose), and Baseline (Screening).

A descriptive summary table will be presented for ALT values, change from Baseline and percentage change from Baseline in ALT by treatment group and visit using the 8-number summary. Percent change from baseline will be analyzed similarly as the change results.

Change from Baseline in ALT at Week 12 will be analysed using an ANCOVA model with treatment as a fixed effect and the associated Baseline value as a covariate. Least squares means and standard errors will be presented for each visit, p-value and 2-sided 95% confidence interval for treatment differences will be presented for each visit. Significance tests will be based on least-squares means using a two-sided $\alpha = 0.05$. As an additional analysis, the primary endpoint will be analysed using the Multiple Imputation method as described in section 7.2.1.

A by-subject listing will be provided for observed and derived variables.

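### The SAP does not fix one primary ALT analysis: the missing-data rule departs undeclared from the protocol, the imputation model is unspecified, and three ALT baselines are unranked

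*SAP*

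**What the plan says.** **Missing data.** For the primary ALT endpoint, Protocol 11.6 says "Multiple Imputation (MI) will be used to impute missing data" and leaves the details to the SAP. SAP 7.3.1 opens with a general rule that "missing data for the primary endpoint and secondary endpoint are not imputed, with the exception being a secondary analysis on the primary endpoint". Two sentences later it says, without qualification, "All missing Week 12 values for the primary efficacy endpoint will be estimated by multiple imputation (MI"). SAP 8.6.2 states "All subjects in the efficacy population will be included, with a secondary analysis" on the per protocol set, and then: "As an additional analysis, the primary endpoint will be analysed using the Multiple Imputation method as described in section 7.2.1". The MI text is in fact in 7.3.1. It describes MCMC in general terms ("The goal of the imputation step is to draw random samples of missing data based on information contained in the observed data") and says that "missing data will be imputed m times to produce m sets of complete data". It names no imputation variables or visits and gives neither a value for m nor a seed. SAP Section 9 lists only PK and C4 outputs by pruritus status.

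**Baseline.** SAP 8.6.2 derives ALT baseline as an average, as the last pre-dose value and as the screening value, and runs the ANCOVA on whichever applies. None is called primary. The footnote to the visit-window table in SAP 7.2 averages all pre-dose laboratory values, while Table 3 averages screening and Day 1 only.

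**Model.** SAP 3.2.1 stratifies randomisation by prior liver biopsy. The ANCOVA in SAP 8.6.1 and 8.6.2 contains treatment and baseline only.

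**The concern.** Two statisticians working faithfully from these documents could report different main ALT results. There are two missing-data rules and three baselines, so six candidate analyses, and no sentence picks one.

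The missing-data rule matters for more than labelling. An unimputed ANCOVA drops every subject without a Week 12 ALT, which does not fit the statement that the whole efficacy population is included. If loss depends on ALT seen during treatment and differs between arms, the estimate can be biased. MI helps only if it uses that interim ALT, and the SAP does not say that it will.

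Once the blind is broken, a choice among six results can no longer be shown to be independent of the data.

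**Working it through.** **1. The plan's own figure.** SAP 5 and Protocol 11.2 give 44 per dose, 22 placebo, difference 30, SD 40, two-sided 0.05. The standard error is 40 × √(1/44 + 1/22) = 10.4. Power from the noncentral t with 64 degrees of freedom is 80.76%, against the stated 80.438%. The figure reproduces closely, and 10.4 is the yardstick below.

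**2. Who lacks a Week 12 value.** The SAP 7.2 window runs from Day 71 to end of treatment + 7. It is empty when end of treatment + 7 < 71, that is, when treatment ends before Day 64. An early end-of-treatment visit then cannot supply Week 12. Planned discontinuation is 10% (SAP 5) or 20% (Protocol 11.2), i.e. 12.5 or 25 of 125; not all of these need stop before Day 64. ALT is scheduled at Weeks 2, 4 and 8 (Protocol Table 19).

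**3. What the missing-data rule can change.** The documents give no loss mechanism or correlations, so these are assumed: true effect −30, ALT SD 40, baseline-to-post correlation 0.4 or 0.5, adjacent-visit correlation 0.5 or 0.75, and loss after Week 2, 4 or 8 with logistic slope 1.5 per SD of the latest ALT. Arms are 50/50/25, with 1,500 simulated trials per setting.

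| Loss mechanism | Unimputed ANCOVA |
|---|---|
| Random, or driven by baseline | −29.6 to −30.2, no bias |
| Interim ALT, active arms only | shift 1.2–2.5 IU/L at 10% loss, 2.4–4.9 at 20% |
| Interim ALT, placebo at half the active rate | shift 0.5–1.3 and 1.1–2.4 |
| Interim ALT, equal rates | shift 0.2 or less |
| Unseen high Week 12 ALT, active only | −33.7 to −38.1 |
| Unseen high Week 12 ALT, placebo at half rate | −31.5 to −34.0 |

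The interim-ALT shifts are measured against MI that uses interim ALT. They go either way, depending on whether high or low ALT drives loss. MI with Week 2, 4 and 8 ALT gives −29.3 to −30.6 when loss follows interim ALT. It does not cure loss driven by unseen Week 12 ALT (−32.3 to −36.7 active only; −30.8 to −33.0 with placebo at half rate).

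Equal rates are not the same as one common rule. In large-sample runs, the same interim-ALT rule in both arms gave about −26 to −29. A rule removing high values took more placebo than active subjects (21% against 10%, or 36% against 20%), because the drug is assumed to lower ALT.

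**4. Why the imputation variables decide the matter.** With treatment and baseline alone, imputed values are drawn from the same regression that the ANCOVA fits, so they add no information. In simulation the result stayed within 0.1 IU/L of the unimputed one. With m unstated, simulation noise is the between-imputation SD over √m. For an SD of 2.0 to 3.5 this is 0.9–1.6 IU/L at m = 5 and 0.4–0.8 at m = 20.

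**5. Baselines.** Mean estimates from the three agree within 0.15 IU/L over repeated trials (screening–Day 1 correlation 0.5–0.9, baseline–Week 12 correlation 0.3–0.7). Within one trial, the average-based and last-value estimates differ with an SD of 1.1–2.6. The p < 0.05 verdict differs among the three baselines in 2.1–7.7% of trials at a true −30, and among all six analyses in 5.1–14.5%. If any of the three baselines were allowed to count, per-dose type I error would be 5.3–10.6%.

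**6. Stratum.** SE ratio = √(1 + gap² × p(1−p)/32²), with residual SD 32 and stratum share p of 0.2 or 0.4 (assumed). A residual ALT gap between strata of 5–10 IU/L enlarges the SE by 0.2–1.2%, and a gap of 20 by 3.1–4.6%.

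**The case against.** A reader might infer that the SAP flatly contradicts itself on MI. The text does not force that. The opening rule in 7.3.1 allows a secondary analysis of the primary endpoint, the later MI sentences can be read as describing it, and 8.6.2 calls MI additional. Unimputed ANCOVA as main with MI in support is a consistent reading. What survives is that this reading departs from Protocol 11.6 and sits badly with the inclusion of the whole efficacy population.

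The conflict with the protocol is also mild. Protocol 11.6 defers details to the SAP, the protocol synopsis gives the ANCOVA without MI, and SAP Section 1 provides for non-principal changes: "Any other change to the data analysis methods described in the protocol, and the justification for making the change, will be described" in the study report. Silence in Section 9 is therefore not in itself a breach. But a report written after unblinding cannot settle in advance which result is primary.

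On baselines, the last-value rule in SAP 8.7.3 belongs to the safety analyses, and the Day 1 wording in Protocol 7.1.3 is a visit description. The 7.2 footnote is a partial default and matches Table 3 unless ALT has an extra pre-dose value. Even so, 8.6.2 specifies three for this endpoint and ranks none.

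A reader might also infer inflated type I error, or that the ALT/AST stopping rules will bias the trial. The SAP nowhere lets the best of three baselines count. No document figure supports 10–20% loss through the stopping rules, and post-baseline ALT is blinded unless flagged (Protocol 6.1.1).

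Finally, naming any one baseline and any one missing-data rule would end the ambiguity. MI, the average baseline and the stratum are further choices, made for the reasons under the fix.

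**Conclusion.** The concern holds as a specification gap that should be fixed; it does not show that the trial is biased. Confidence is high on the text and low on the sizes, which rest on assumed mechanisms and correlations.

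- **Missing data.** The unimputed ANCOVA is unbiased if loss is random, depends only on treatment and baseline, or follows ALT at equal rates in the arms. If ALT-related loss differs between arms, including under one common rule when the drug lowers ALT, the shift is roughly 1 to 5 IU/L at 10–20% active loss, below the design SE of 10.4. Loss driven by unseen Week 12 ALT can shift it by up to 8.1 (−38.1 against −30), and MI does not remove that.
- **Baseline.** This is an open choice among estimates of the same effect. Type I error of about 5–11% would arise only under a best-of-three rule that the SAP does not state.
- **Stratum.** Leaving it out costs a little precision and errs on the conservative side.

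**What to change.** Before database lock, amend SAP 7.3.1 and 8.6.2 to name one primary analysis:

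- ANCOVA of Week 12 ALT change on treatment, one named ALT baseline and the prior-biopsy stratum. The pre-dose average agrees with the 7.2 footnote; define it identically there and in Table 3.
- Missing Week 12 ALT handled by MI, in line with Protocol 11.6, from treatment, baseline, stratum and Week 2, 4 and 8 ALT, with the number of imputations and the seed stated.
- The unimputed ANCOVA and the other two baselines labelled as sensitivity analyses.
- The added stratum, and any other departure from the protocol, recorded in Section 9. Correct the 7.2.1 cross-reference to 7.3.1.

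The cost is one degree of freedom for the stratum and a little programming. All the data are already scheduled. MI of this kind still assumes that loss is explained by observed values, so the SAP should not present it as protection against loss driven by unseen Week 12 ALT.
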